5.8.2 Clinical Laboratory Evaluations

The list of all protocol specified clinical laboratory safety tests (serum biochemistry, safety haematology and urinalysis) is given in Appendix A Table 6. Laboratory safety tests will be performed at each study visit in accordance with the Schedule of Events in Section 2.3. For tabulations, analysis windows (see Section 5.1.2) are considered for each visit.

Clinical laboratory tests are planned to be performed by central laboratory. However, in case of pandemic (e.g., COVID-19) related restriction and impossibility of sample shipment, or inability of subject to visit the site or inform the Medical Monitor of the study, the laboratory assessments may be performed in a local laboratory at site or near to subject's home. If any, the total number of values tabulated provided from a local laboratory will be indicated in the footnote of tables.

All laboratory data will be reported in standard international (SI) units. All quantitative values for haematology and serum biochemistry parameters at each assessed visit will be compared with the relevant reference range in SI and categorized as:

- Low: Below the lower limit of the reference range.
- Normal: Within the reference range (upper and lower limits included).
- High: Above the upper limit of the reference range.

For analysis purposes, values preceded by a “<” or a “>” sign (i.e. those below or above the limits of quantification) will be considered equal to the lower or upper limit of quantification, respectively.

For all haematology and serum biochemistry parameters displayed in Appendix A Table 6, descriptive statistics will be performed on a continuous scale for the values by visit (from baseline) and for changes from baseline by post-baseline visit for actual treatment groups on the safety set. This analysis will be repeated on the ITT, PPS and mITT if applicable (see Section 4.4 for the mITT definition). Urinalysis results will only be listed on the aITT. Abnormal haematology and serum biochemistry results (defined as results below or above reference range) will also be listed separately on the safety set.

The number and percentage of subjects within each categorized shift relative to the reference range (low, normal and high) at baseline compared to each post-baseline visit for haematology and serum chemistry will be tabulated by actual treatment groups on the safety set. Subject with missing values will be classified in a missing category.

All laboratory results (serum biochemistry, safety haematology and urinalysis) will be listed, including all unscheduled visits for the aITT.

In addition, listings will be provided for urine Pregnancy Test and for hemoglobin local laboratories measurements.

5.8.3 *Electrocardiogram (ECG) Evaluations*

PR interval (ms), QRS duration (ms), QT interval (ms), RR interval (ms), QTcF (ms) interval and ventricular rate (bpm) will be evaluated at each visit at pre-dose and 2 hours (± 30 minutes) post-morning dose.

QT corrected using Fridericia formula is defined as:

$$QTcF(ms) = QT(ms) / \sqrt[3]{RR\ (ms)}$$

Pre-dose and 2 hours post morning dose values will be described by visit from baseline as well as changes from baseline (pre first dose measures) to each post baseline measures at pre-dose and at 2 hours post morning dose for all parameters by actual treatment groups on the safety set. For tabulations, analysis windows (see Section 5.1.3) will be considered for each visit but no window will be considered for the time-points (pre or 2 hours post-dose).

For each ECG parameter, the following figure will be provided: individual values (y-axis) in function of target visit day and time-point (nominal x-axis scale: "D1", "D1+2h etc...") joined by subject and plotted in separate windows for the randomised cohorts (1, 2, 3, 4) and for overall subjects randomised in VIT-2763 (5-window panel plot). All graphics will be done on the Safety set.

All ECG parameters results will be listed with changes from baseline as well as overall ECG interpretation on the aITT.

5.8.4 *Vital Signs and Body Weight Evaluations*

The values and changes from baseline results of Systolic Blood Pressure (SBP) (mmHg), Diastolic Blood Pressure (DBP) (mmHg), pulse rate (bpm) and body weight (kg) will be summarised by visit by actual treatment groups on the safety set. For tabulations, analysis windows (see Section 5.1.3) will be considered for each visit.

Vital sign results with changes from baseline will be presented for individual subjects in data listings on the aITT.

5.8.5 *Physical Examinations*

All clinically significant abnormalities in physical examination will be collected in the general medical history or the adverse event eCRF pages as appropriate. Therefore, no specific analysis of physical examination will be performed.

5.9 *Other Analyses*

5.9.1 *Iron-related parameters and blood inflammatory markers*

Iron-related parameters include total serum iron, serum ferritin, transferrin, TSAT, hepcidin and erythropoietin.

Blood inflammatory markers include high sensitivity C-reactive protein, interleukin 1 and interleukin 6, tumour necrosis factor alpha, soluble vascular cell adhesion molecule 1, endothelin-1, soluble platelet-selectin, and xanthine oxidase.

All data will be reported in SI. For analysis purposes, values preceded by a “<” or a “>” sign (i.e. those below or above the limits of quantification) will be considered equal to the lower or upper limit of quantification, respectively.

For all iron-related parameters and blood inflammatory markers, standard descriptive statistics for continuous variables will be tabulated for the values by visit (including baseline) and for changes from baseline by post-baseline visit for randomised treatment groups as described in Table 5 on the ITT. Analysis windows (see Section 5.1.3) will be considered for each visit.

Analyses will be repeated on the PPS by actual treatment group if it differs and on mITT if applicable.

For each iron-related parameter and blood inflammatory marker, the following figure will be provided: individual values (y-axis) in function of target visit day (x-axis) joined by subject and plotted in separate windows for the randomised cohorts (1, 2, 3, 4) and for overall subjects randomised in VIT-2763 (5-window panel plot). All graphics will be done on the ITT.

Finally, all parameter results with changes from baseline will be listed, including all unscheduled visits, for the aITT.

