1.2.1.1 Absorption, Distribution, Biotransformation, and Elimination

The oral bioavailability depends on species and dose; it ranged from 16 to 51% in rats and up to 85% in dogs. Higher than proportional plasma concentrations with increasing dose could be due to nonlinear excretion, resulting from saturation of clearance.

Distribution in rats was widespread, with the highest measured tissue radioactivity at 1 hour post-dose. Rapid accumulation was observed in particular in the kidney pyramid, but also in the adrenal medulla and mammary glands (females). Twenty-four hours post-dose, radioactivity was not detectable or at very low levels with the exception of adrenal medulla, preputial gland, and mammary tissues.

In vitro, VIT-2763 was shown to be a substrate of P-glycoprotein, organic anion transporter 3, multidrug and toxin extrusion transporter 1 (MATE1) and MATE-2K, and likely also of the organic cation transporter 1 (OCT1) and OCT2. In vitro studies in human hepatocytes have shown that VIT-2763 is mainly metabolised by CYP 3A4 and to some extent by CYP 2D6. VIT-2763 showed high clearance in rats and moderate clearance in dogs, both in vitro and in vivo. In human hepatocytes and liver microsomes, low levels of metabolism have been observed. The abundance of individual metabolites was different across species, whereby the metabolites in the human in vitro samples (one of them being unique to human) were all detected with low quantities.

Mass balance data in rats revealed primary excretion in urine (53.7% of total radioactive dose) and bile (20.6% of total radioactive dose). No parent VIT-2763 was detected in another bile duct cannulated rat study indicating that VIT-2763 metabolites or conjugation products are excreted in bile. The majority of the radioactivity in urine and bile accumulated within 8 hours and the vast majority of the radioactivity was eliminated within 24 hours of dose administration. The second peak observed in rat plasma was less pronounced in bile duct cannulated compared to non-bile duct cannulated animals, suggesting that enterohepatic circulation occurs.

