12.9 Safety Evaluations

All safety analyses will be performed on the safety set.

Adverse Events

Only TEAEs defined as events with an onset date later or on the same date as first IMP intake will be tabulated. AEs that occurred during the study but before first IMP intake will be only listed.

Summary tables with the counts and percentage of subjects and the number of events will be provided on overall subjects receiving VIT-2763, by dose group and on all subjects receiving placebo for any TEAEs, any severe TEAEs, any serious TEAEs, any TEAEs leading to study withdrawal and any TEAEs leading to death.

All AEs will be coded according to a standard dictionary (MedDRA).

Tables of the counts and percentages of subjects with at least 1 TEAE by SOC and PT will be provided for all TEAEs and TEAEs by severity and by relationship over 8 weeks of treatment (secondary endpoint) and up to 4 weeks after EoT. Similar tables will be provided for serious TEAEs, TEAEs leading to premature discontinuation of the study and TEAEs leading to death.

Clinical Laboratory Tests

Values by visit from baseline and changes from baseline by post-baseline visit for the haematologic, biochemistry, and urinalysis parameters will be summarised on overall subjects receiving VIT-2763, by dose group and on all subjects receiving placebo.

Shift tables crossing counts of baseline values lower, within and higher than laboratory normal range with the counts of each post-baseline visit will be provided for the haematologic, biochemistry, and urinallysis parameters on the same treatment groups.

Vital Signs and Body Weight

Values by visit from baseline and changes from baseline by post-baseline visit for blood pressure, pulse rate, and body weight will be summarised on overall subjects receiving VIT-2763, by dose group and on all subjects receiving placebo.

ECGs

Values by visit from baseline and changes from baseline by post-baseline visit for PR interval, QRS duration, QT interval, and QTcF interval will be summarised on overall subjects receiving VIT-2763, by dose group and on all subjects receiving placebo.

Abnormal ECG findings will be listed.

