- 6 Only in females of childbearing potential.
- 7 Urinary dipstick including pH, protein, glucose, ketone, RBCs, and WBCs. Quantitative measurement only if positive dipstick. Urinalysis includes also (at Visits V1, V2, V4, and V6) urinary microalbumin, creatinine, and microalbumin/creatinine ratio (spot sample, morning void).
- 8 Haematology panel/RBC indices sampled at pre-dose (trough) include: Hb, reticulocytes (abs, %), RBC count, HCT, MCH, MCV, MCHC, RDW, % hypochromic RBC, CHCM, WBC, neutrophils (abs, %), lymphocytes (abs, %), monocytes (abs, %), eosinophils (abs, %), basophils (abs, %), and platelets. At screening/Visit V1, only Hb and reticulocytes will be assessed.
- 9 Serum chemistry sampled at pre-dose (trough) includes calcium, sodium, magnesium, potassium, phosphorus, chloride, bicarbonate, blood urea nitrogen, uric acid, creatinine kinase, creatinine, folic acid, albumin, total protein, globulin (calculated), alanine transaminase, aspartate transaminase, alkaline phosphatase, glucose, triglycerides, and cholesterol.
- 10 Haemolysis markers sampled at pre-dose (trough) include LDH, free haptoglobin, and direct/total bilirubin (indirectly calculated).
- 11 Endothelial inflammation/dysfunction markers sampled at pre-dose (trough) include hsCRP, IL-1, IL-6, TNF-alpha, sP-selectin, sVCAM-1, xanthine oxidase, and endothelin-1.
- 12 Iron-related parameters/markers of erythropoiesis sampled at pre-dose and 2 hours post- morning dose include total serum iron, serum ferritin, transferrin, TSAT, hepcidin, and erythropoietin. At Visit V1, serum ferritin, TSAT, and TIBC will be sampled for exclusion criteria only.
- 13 PK samples are collected on Visit V4 at pre-dose, and 2 hours (± 15 minutes), 4 hours (± 30 minutes), and 6 hours (± 30 minutes) post-dose.
- 14 At Visit V2, the subject will be asked for VOC episodes within the last 8 weeks. At Visits V3, V4, V5, and V6, the subject will be asked for VOC episodes (number of events and pain intensity (NRS: 0-10) compared to historical VOC episodes) since previous visits. Visceral infarctions will be assessed as per standard of care.
- 15 For more details see the respective visit in Section 8 of CSP.

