2.6.3 Exploratory Endpoint(s)

- Changes in haemolysis markers as measured by indirect, direct, and total bilirubin, LDH, potassium, Hb, and free haptoglobin, from baseline after 2, 4, and 6 weeks of treatment and 4 weeks after end of treatment (EoT).
- Frequency and severity of reported or observed AEs by SOC and PTs using MedDRA coded terms, indicating seriousness criteria and relatedness up to 4 weeks after EoT.
- Changes in clinical laboratory safety tests (serum biochemistry, safety haematology, and urinalysis) from baseline, 12-lead ECG, physical examination findings, vital signs (blood pressure, pulse rate), and haematological changes due to iron-restricted erythropoiesis after 2, 4, 6, and 8 weeks of treatment and 4 weeks after EoT.
- Changes in haematological indices, including Hb concentration, RBC count, Hct, MCV, MCH, MCHC, CHCM, RBC distribution width, WBC analyses including differential WBC counts, platelet and reticulocyte counts, percentage reticulocytes, percentage hypochromic microcytic RBCs (RBC volume versus Hb scatterplot analysis), from baseline after 2, 4, 6, and 8 weeks of treatment and 4 weeks after EoT.
- Changes in blood inflammatory markers as measured by high sensitivity C-reactive protein, interleukin 1 and interleukin 6, tumour necrosis factor alpha, soluble vascular cell adhesion molecule 1, endothelin-1, soluble platelet-selectin, and xanthine oxidase, from baseline after 2, 4, 6, and 8 weeks of treatment and 4 weeks after EoT.
- Assessment of iron-related parameters and markers of erythropoiesis: total serum iron, serum ferritin, serum transferrin, calculated TSAT, hepcidin, and erythropoietin, from baseline after 2, 4, 6, and 8 weeks of treatment and 4 weeks after EoT.
- VIT-2763 PK parameters (maximum concentration (C_{max}), clearance, distribution volume, area under the curve (AUC)). Sparse sampling for determination of VIT 2763 plasma concentration following multiple dosing will be obtained from pre-dose trough to 2 hours, 4 hours and 6 hours post-morning dose at study Visit V4. A population PK approach will be applied to estimate PK parameters.

- Change in patient reported outcomes using ASCQ-Me from baseline after 2, 4, 6 and 8 weeks of treatment.
- Changes in abnormal RBCs (sickling) assessed by peripheral blood smear from baseline after 2, 4, 6 and 8 weeks of treatment and 4 weeks after EoT.
- Number of VOC episodes and visceral infarctions over 8 weeks of treatment and 4 weeks after EoT.

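### SAP 5.8.2 lists urinalysis without tabulating it, so the urinalysis part of an exploratory safety endpoint, including the urine microalbumin/creatinine ratio, has no by-arm summary

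*SAP*

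**What the plan says.** The endpoint list in SAP 2.6.3 includes, as one exploratory item, "Changes in clinical laboratory safety tests (serum biochemistry, safety haematology, and urinalysis) from baseline", together with ECG, physical examination, vital signs and haematological changes. Protocol 3.6 has the same item.

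Protocol 12.9 says how it is to be analysed: values by visit and "changes from baseline by post-baseline visit for the haematologic, biochemistry, and urinalysis parameters will be summarised" for all VIT-2763 subjects, by dose group and for placebo. It adds shift tables against the normal range for the same three laboratory groups. All safety analyses are on the safety set.

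SAP 5.8.2 is narrower. Its continuous summaries are introduced with "For all haematology and serum biochemistry parameters displayed in Appendix A Table 6, descriptive statistics will be performed on a continuous scale". Its shift tables compare the reference-range category "at baseline compared to each post-baseline visit for haematology and serum chemistry will be tabulated by actual treatment groups on the safety set". For urine the rule is "Urinalysis results will only be listed on the aITT". A later sentence in the same section gives the general listing: "All laboratory results (serum biochemistry, safety haematology and urinalysis) will be listed, including all unscheduled visits for the aITT".

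The schedule footnote in SAP 2.3 shows that urinalysis is more than a dipstick: "Urinalysis includes also (at Visits V1, V2, V4, and V6) urinary microalbumin, creatinine, and microalbumin/creatinine ratio". SAP Appendix A Table 6 puts those three quantities in its urinalysis column.

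SAP 1.2, on changes from the protocol, mentions only additional analysis sets. SAP 1 gives the SAP precedence where the two documents differ.

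**The concern.** The SAP names a change from baseline among its endpoints and then specifies no analysis that produces it. Because the SAP prevails, the protocol's plan for urinalysis falls away, and a reader who checks SAP 1.2 for departures will not find this one.

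For semi-quantitative dipstick items, a listing may be all that is useful. The microalbumin/creatinine ratio is different: it is continuous and is scheduled for every subject at baseline and at two on-treatment visits, alongside a concurrent placebo group. Under the SAP it gets no by-arm value and no by-arm change. At stake is a component of an exploratory safety endpoint that would reach the study report as individual data only.

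**Working it through.** No power, alpha or effect-size figure bears on this point. The check is a comparison of texts and a count.

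**Step 1: what each place provides for urinalysis**

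| Output | Protocol 12.9 | SAP 5.8.2 |
|---|---|---|
| Values by visit, by arm | Yes | No (haematology and biochemistry only) |
| Change from baseline, by arm | Yes | No (haematology and biochemistry only) |
| Shift tables | Yes | No (haematology and chemistry only) |
| Separate listing of abnormal results | Not mentioned | No (haematology and biochemistry only) |
| Listing of results | Not mentioned | Yes, on the aITT |

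**Step 2: does the listing-only rule reach the ratio?** Yes. Table 6 classes the ratio as urinalysis. No other SAP section summarises it: baseline characteristics (5.3) omit it, and the haemolysis, iron, inflammatory and sickling analyses (5.7, 5.9.1, 5.9.2) concern other parameters.

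**Step 3: does the listing supply the endpoint?** Not as specified. The laboratory listing in 5.8.2 does not mention change from baseline, whereas the ECG and vital-sign listings (5.8.3, 5.8.4) do. The listing is also on the aITT, which SAP 4.4 presents by randomised treatment and which takes in any protocol version. Protocol 12.9 calls for the safety set, analysed by treatment received (Protocol 12.4.3).

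**Step 4: count of values affected**

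Inputs: 24 subjects allocated 3:3:3:2:1 (SAP 2.5), which gives 6 + 6 + 6 = 18 active and 4 + 2 = 6 placebo, pooled (SAP 5.1.5). The ratio is scheduled at V1, V2, V4 and V6 (SAP 2.3). V1 and V2 precede treatment, so V4 and V6 are the only post-baseline visits. The count assumes no dropout, missed samples or replacements.

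- Post-baseline values: 24 × 2 = 48
- Active: 18 × 2 = 36
- Pooled placebo: 6 × 2 = 12
- For context, with V2 as baseline: 24 × 3 = 72; with screening as well: 24 × 4 = 96

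The 48 post-baseline values carry the change from baseline, so they measure the gap. Under SAP 5.8.2 none of them enters a by-arm table.

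**The case against.** The case for leaving the SAP alone has substance.

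- **The choice looks deliberate.** The word *only* in 5.8.2 is explicit, and the protocol leaves detailed methodology to the SAP. SAP 5.8.5 likewise drops a separate analysis of physical examination, which belongs to the same endpoint item. This stands in part. However, 5.8.5 gives a reason and 5.8.2 gives none, SAP 2.6.3 still promises change in urinalysis, and SAP 1.2 does not mention the departure.
- **The data stay visible.** Listings are ordered by dose and then placebo (SAP 5.1.5), and with six subjects per group a reader could tabulate the ratio by hand. Clinically significant laboratory results that meet the criteria in Protocol 10.5.4 are reported as AEs, an unblinded DSMB reviews safety, and no decision rule depends on the table. All of this stands, and it keeps the point minor.
- **Shift tables fit dipsticks poorly.** The protocol's lower, within and higher categories do not suit semi-quantitative results without a further scheme. This stands, and the fix allows for it.

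A reader might infer more than the documents support, in three ways.

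- *A declared safety endpoint has no result.* The item is exploratory and composite. Its biochemistry, haematology, ECG and vital-sign parts are summarised by arm; the gap claimed here is the urinalysis part.
- *Renal safety goes unsummarised.* Serum creatinine and blood urea nitrogen are in Table 6 and receive values, changes and shift tables by actual treatment. Nor is the ratio the only possible quantitative urine result, since a positive dipstick also triggers quantitative measurement.
- *The nonclinical data point to a renal hazard.* Protocol 1.2.1.1 does say "Rapid accumulation was observed in particular in the kidney pyramid" and reports 53.7% of the radioactive dose in rat urine. It then reports radioactivity at 24 hours as very low or undetectable except in adrenal medulla, preputial gland and mammary tissues; kidney is not among the exceptions. Urinary recovery describes elimination, not injury. The toxicity summary in Protocol 1.3.1 reports no renal finding, and the cautions in Protocol 7.1 do not name the kidney. These data should not serve as the rationale.

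**Conclusion.** The point holds as an inconsistency between endpoint and analysis. SAP 2.6.3 and Protocol 12.9 call for change from baseline in urinalysis, SAP 5.8.2 provides only a listing, and SAP 1.2 does not declare the difference. The urinalysis component therefore has no by-arm summary, and 48 planned post-baseline ratio values (36 active, 12 placebo) enter no table. The count rests on 24 subjects with complete V4 and V6 samples.

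The priority is low. The endpoint is exploratory, all analyses are descriptive, the groups have six subjects each, and blood-based renal markers are tabulated. The conclusion rests on the mismatch between the sections, not on any suspected renal effect.

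**What to change.** In SAP 5.8.2, add urine microalbumin, creatinine and the microalbumin/creatinine ratio to the continuous summaries: value at baseline, V4 and V6, and change from baseline at V4 and V6, by actual treatment on the safety set, as Protocol 12.9 plans. The standard statistics in SAP 5.1.1 already include the median, minimum and maximum, so no new method is needed.

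Dipstick items may stay as listings. In that case, SAP 1.2 should declare the departure from Protocol 12.9 with a short reason, and SAP 2.6.3 should be aligned so that it does not promise a change from baseline for them.

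The cost is about one extra table from central-laboratory data already collected, plus two small text edits. No additional sampling is required.

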10.5.4 Clinical Laboratory Evaluations

Not every out-of-range laboratory result qualifies as an AE. A laboratory investigation result must be reported as an AE if it is clinically significant and meets any of the following criteria:

- Is accompanied by clinical symptoms
- Results in a change in study treatment (e.g., dosage modification, treatment interruption, or treatment discontinuation)
- Results in a medical intervention (e.g., potassium supplementation for hypokalaemia) or a change in concomitant therapy

- Presents shift of a parameter from a normal value to a pathological value, or results in a deterioration of Common Terminology Criteria grade, or a further worsening of an already pathological value
- Is clinically significant in the Investigator's judgement

It is the Investigator's responsibility to review all laboratory findings. Medical and scientific judgement should be exercised in deciding whether an isolated laboratory abnormality should be classified as an AE. When evaluating such changes, the extent of deviation from the reference range, the duration until return to the reference range, either while continuing treatment or after the EoT with the IMP, and the range of variation of the respective parameter within its reference range, must be taken into consideration.

If, at the end of the treatment phase, there are pathological laboratory values which were not present at baseline, further clinical or laboratory investigations should be performed until the values return to within reference range or until a plausible explanation (e.g., concomitant disease) is found for the pathological laboratory values.

The Investigator should decide, based on the above criteria and the clinical condition of a subject, whether a change in a laboratory parameter is clinically significant and therefore represents an AE. If the Investigator considers such an AE as serious (e.g., medically significant event fulfilling criteria per Section 10.7.1), it must be reported as an SAE.

If a laboratory abnormality meeting the above criteria is a sign of a disease or syndrome only the diagnosis should be recorded in the eCRF.

If a laboratory abnormality meeting the above criteria is not a sign of a disease or syndrome, the abnormality itself should be recorded in the eCRF, along with a descriptor indicating if the test result is above or below the normal range (e.g., "elevated potassium," as opposed to "abnormal potassium").

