Percentages will be calculated using the total subjects per randomised treatment group, except for outputs in the PPS and the safety set, where percentages are based on the total subjects per actual treatment group.

5.1.2 *Definition of Baseline*

The baseline value for a variable will be defined as the last available (non-missing) value before the first administration of study drug. Study day 1 is defined as the day of the first study drug administration. For analysis relative day, if considered date is before the first study drug administration date, then analysis relative day will be computed as date minus first study drug administration date, otherwise, it will be computed as date minus first study drug administration date + 1.

5.1.3 *Planned Assessment Windows*

Table 4 describes the analysis visit windows (i.e. the relative study day ranges) to be applied to the assessments or sample collections dates to determine the analysis visit.

Table 4 Planned and Analysis visits Windows

Analysis Visit Label	Target Day	Planned Visit Window (Protocol Specified)	Analysis Visit Window
Baseline	1	--	Before first IMP intake
Visit 3 (Day 14)	14	± 2 days	From Day 2 to Day 21
Visit 4 (Day 28)	28	± 4 days	From Day 22 to Day 35
Visit 5 (Day 42)	42	± 4 days	From Day 36 to Day 49
Visit 6 (Day 56)	56	± 4 days	From Day 50 to Day 70
Visit 7 (Day 84)	84	± 4 days	From Day 71 and higher

Assessments (planned and unscheduled) will be re-mapped into the analysis windows. For a parameter, the following rules will be applied:

- if several assessments fall into the same analysis window, the closest to the target day will be considered for the analysis.
- When there are 2 assessments closest to the target day, the latest one will be considered for the analysis.
- if several assessments are available at the selected day, the average of the values will be taken.

In all statistical tables by visit, the analysis visits will be considered. In listings presenting data by visit, both nominal and analysis visits will be provided.

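### Laboratory shift tables are by visit with one value per window, so no table shows how many subjects per arm ever shifted, and off-target abnormal results can be left out

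*SAP*

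**What the plan says.** SAP 5.8.2 classifies each haematology and serum chemistry value as low, normal or high. On the safety set, by actual treatment, it then tabulates the "shift relative to the reference range (low, normal and high) at baseline compared to each post-baseline visit for haematology and serum chemistry". Protocol 12.9 plans the same layout: "Shift tables crossing counts of baseline values lower, within and higher than laboratory normal range with the counts of each post-baseline visit". Neither document plans a shift to the lowest, highest or any-time post-baseline value.

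Laboratory tables use the analysis windows of SAP 5.1.3. Unscheduled results are eligible: "Assessments (planned and unscheduled) will be re-mapped into the analysis windows". One value per parameter is then kept. The main rule reads: "if several assessments fall into the same analysis window, the closest to the target day will be considered for the analysis". A tie goes to the later result, and results that share the chosen day are averaged.

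SAP 5.8.2 also plans a listing of all out-of-range haematology and chemistry results (safety set) and a listing of all laboratory results including unscheduled visits (aITT).

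**The concern.** Safety and tolerability is the secondary objective (Protocol 3.2). Protocol 2.3.2 and 2.3.3 rely on two-weekly haematology monitoring to catch excessive pharmacodynamic effects early. The natural summary question is how many subjects in each arm went out of range at any time. The planned tables do not answer it: counts at separate visits cannot be combined without knowing which subjects they refer to.

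The window rule adds a second gap. It selects on timing, not on the result, but extra samples are often taken because something is abnormal. Protocol 5.4.2 has a confirmatory repeat in its transaminase and bilirubin criterion. Protocol 10.5.4 says, of abnormal values at the end of treatment that were absent at baseline, that "further clinical or laboratory investigations should be performed until the values return to within reference range", or until they are explained. Such repeats may show recovery, and the rule can put the recovered value in the table in place of the abnormal one.

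**Working it through.** The plan states no figure for this, so there is none to reproduce. The inputs are the target days, protocol windows and analysis windows in SAP 5.1.3 (Table 4), and six subjects per active cohort and six on pooled placebo (Protocol 6.3.1, Table 2).

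**1. Days that cannot enter.** Suppose the scheduled result exists and lies inside its protocol window. Any result outside that window is then further from target and always loses. For Visit 3 the analysis window is "From Day 2 to Day 21", 20 days, against 5 protocol days.

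| Visit | Analysis window | Length | Protocol window | Length | Excluded days |
|---|---|---|---|---|---|
| 3 | Day 2–21 | 20 | Day 12–16 | 5 | 15 |
| 4 | Day 22–35 | 14 | Day 24–32 | 9 | 5 |
| 5 | Day 36–49 | 14 | Day 38–46 | 9 | 5 |
| 6 | Day 50–70 | 21 | Day 52–60 | 9 | 12 |
| Total | | 69 | | 32 | 37 |

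37/69 = 54%. Of the 37, Days 61–70 (10 days) follow the last dose of any subject whose Visit 6 is in window. That leaves 27 of the 59 days from Day 2 to Day 60 (46%).

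**2. Results that drop out.**
- Early termination: a termination sample on Days 17–21 is mapped to the Visit 3 window. It is 3 to 7 days from target, and an in-window Visit 3 sample is at most 2, so the termination sample is never used.
- Displacement: a Visit 6 value on Day 53 is |53 − 56| = 3 days from target and a repeat on Day 58 is 2, so the repeat is used.
- Tie: Day 54 and Day 58 are both 2 days away, so the later is used.

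**3. How often an unscheduled value does enter.** Let the scheduled result be d days from target. The days that beat it number 2d − 1 (strictly closer), plus one (tied and later) if it was early. Summed over a protocol window of ±w days, this is Σ(4d − 1) = 2w² + w, which is 10 for w = 2 and 36 for w = 4. Divide by (2w + 1) × window length. This assumes that scheduled days are uniform over the protocol window and unscheduled days uniform over the analysis window.
- Visit 3: 10/(5 × 20) = 10%
- Visits 4 and 5: 36/(9 × 14) = 29%
- Visit 6: 36/(9 × 21) = 19%
- Visit 7: 36/(9 × 27) = 15%, if its open window is assumed to end on Day 97

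If every visit is exactly on target, the figure is 0% for a result from another day. Under the same assumption for scheduled days, a repeat 1 to 7 days later in the same window replaces the scheduled value in 6/32 = 19% of pairings at Visit 3, 19/53 = 36% at Visits 4 and 5, and 19/63 = 30% at Visit 6.

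**4. What by-visit counts leave open.** In an arm of six, one High at each of Visits 3 to 6 may be the same subject four times (1/6 = 17%) or four different subjects (4/6 = 67%). The table cannot tell which.

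**The case against.** Four arguments weigh against the point.

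- **Listings.** With 24 planned subjects, the two listings let a reader find every affected subject by hand and would settle the 1/6 or 4/6 example. That stands. But a listing gives no proportion per arm, and the abnormal-result listing holds any out-of-range value, not only shifts. Inclusion needs an absolute or percentage reticulocyte count above 1.5 × ULN and exclusion caps haemoglobin (Protocol 5.2, 5.3), so it will probably hold many values already abnormal at baseline.
- **Adverse events.** Under Protocol 10.5.4 a clinically significant laboratory result that meets a listed criterion is an adverse event, and SAP 5.8.1 counts each subject once per term, with tables by maximum severity. That gives an ever-affected count, but only for results the investigator judges significant.
- **Status.** The secondary safety endpoint is adverse events. Laboratory changes are exploratory, everything is descriptive, and by-visit shifts match Protocol 12.9. So this is a gap in the output, not an inconsistency or an error.
- **Eligibility.** A reader might infer that unscheduled results almost never reach the tables. SAP 5.1.3 does not support that. They enter when closer to target, when tied and later, when averaged on the selected day, or when the scheduled value is missing.

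**Conclusion.** The point holds as a modest, cheap improvement. The shift tables are by visit only, one value is kept per window, and no table counts subjects ever shifted. Following the rule exactly can leave out an off-target unscheduled or early-termination abnormality, or replace an abnormal scheduled value with a later normal one.

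The firm figure is 37 of 69 window days from which results cannot enter. It assumes that the scheduled result is present and inside its protocol window. It counts days, not samples, and includes days after the last dose. The documents give no frequency of unscheduled testing, so the number of results lost cannot be derived. The 0% to 29% entry rates rest on the assumed visit timing.

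A reader might also infer that the plan undercounts affected subjects. It does not: a count at a visit is a statement about that visit's selected values, and no ever-affected count is reported that could be wrong. The highest single-visit count is only a lower bound if it is read that way.

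**What to change.** Keep the by-visit tables. In SAP 5.8.2, add baseline-to-worst post-baseline shift columns on the safety set, with lowest and highest values handled separately. Use all scheduled, unscheduled and early-termination results, including local results used in place of central ones, from first dose through Visit 6/ET and, separately, through Visit 7. Count each subject once per parameter and arm. State whether the routine local haemoglobin safety measurements, which the SAP only lists, count towards these columns.

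Correct the window cross-reference in 5.8.2 from 5.1.2 (baseline definition) to 5.1.3 (windows). SAP 5.7.1 has the same slip.

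The cost is a short SAP edit, a few table columns and minor programming, with no new data. There are two limits. Worst-value counts rise with the number of samples per subject, so a footnote should give the number of results per arm. Parameters already out of range at baseline for most subjects will gain little.
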